2.1 Trial Diagram

3.0 OBJECTIVES & RATIONALE

Primary Objective

1. Determine the sensitivity and specificity of relative cerebral blood volume (rCBV) measured by steady state MRI with ferumoxytol in predicting true vs pseudoprogression after SRS and intravenous (IV) pembrolizumab in subjects with brain metastases from NSCLC.

Rationale: This study is not powered to test any formal hypothesis and we aim to collect preliminary data on the sensitivity and specificity of rCBV measurements with ferumoxytol in the primary objective.

Secondary Objectives

1. Evaluate the safety and tolerability of pembrolizumab when given with SRS in subjects with brain metastasis.
2. Evaluate progression free survival, overall survival, best response in brain disease, best response in systemic disease, and duration of best responses of brain and systematic diseases.

Rationale: Given the small sample size, we aim to collect preliminary data on survival, safety, tolerability and efficacy of pembrolizumab when given with SRS in subjects with brain metastasis. No additional toxicity profile is expected when pembrolizumab is used in combination with SRS and ferumoxytol. Toxicities will be evaluated using CTCAE version

4.0. Subjects will have ongoing toxicity evaluation, with documentation of infusion related reactions (grade 3, 4), hematologic toxicities (grade 3, 4) and all other grade 3, 4 toxicities. Each toxicity will be attributed to pembrolizumab and ferumoxytol or neither/both.

Exploratory Objectives

1. Compare the immune response as determined by the volume, pattern and intensity of delayed (24hr) ferumoxytol uptake between subjects who develop true vs pseudoprogression.
2. Investigate the serum immunological parameters and correlate clinical as well as radiological response with systemic immune response to pembrolizumab as measured by immunological panel.
3. Compare the changes percentage expression in PDL-1 in the biopsy tissue before and after therapy at the time of progression.
4. In subjects with measurable systemic lesions, investigate the feasibility of measuring vascular volume fraction (VVF), vessel size index (VSI) and vessel density index (VDI) as surrogate for response (true vs. pseudoprogression, as measured with RECIST 1.1 criteria).

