Rationale for Exploratory Objectives: This study is not powered to test any formal hypothesis and we aim to collect preliminary data regarding the exploratory endpoints that will enable us to better understand the tumor biology of brain metastases and PD-1 expression and interaction with PD-1 inhibitors. In addition, this pilot study will enable us to collect preliminary data on efficacy of pembrolizumab on brain metastases.

Evidence of up-regulation of the immune system is expected in the tumor micro-environment as well as systemically in subjects that develop pseudoprogression and respond favorably to pembrolizumab.

- 1) Local immune up regulation in the tumor microenvironment will be characterized by increased delayed ferumoxytol uptake, the total volume of T1 intensity 24 hours after ferumoxytol administration will be measured and correlated with compared to response to therapy. Ferumoxytol is taken up by activated inflammatory cells including macrophages. An increased uptake on delayed scans suggests a robust inflammatory response. We expect greater intensity and magnitude of delayed ferumoxytol uptake signal in subjects who develop pseudoprogression and not in those that have true tumor progression.
- 2) PD-L1 expression and the type of immune cells present in the tumor microenvironment will be compared between archival biopsy tissue and brain tumor tissue obtained before initiation of pembrolizumab and at the time of progression.
- 3) Systemic immune up regulation will be measured by the blood immunological assay as described in (section 8.5). Clinical outcomes will correlate with T cell activation/phenotype, increases in systemic inflammatory markers will be associated with outcomes.
- 4) In a subset of subjects with measurable systemic disease, response to therapy in the systemic disease will be monitored by measuring changes in tumor microvasculature

by MRI imaging of the lesion of interest that will precede changes in tumor response as measured by traditional RECIST 1.1 and immune-related response criteria (irRC). We expect that changes in tumor microvascular will provide a more accurate determination of tumor immune flare versus true progression as determined by immune response criteria

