7.2 Study procedures narrative

Enrolled subjects will receive pembrolizumab (200 mg I.V. every 3 weeks) starting on the first day of radiation (\pm 15 days) until persistent radiographic progression is confirmed. [Subjects may receive standard of care cytotoxic chemotherapy \(carboplatin and pemetrexed\) while on trial, at the treating physician's discretion.](#) [72, 73] MRI scans will be performed to assess response to therapy. Clinical standard of care MRIs are done at baseline, 12 weeks post radiation and then every 9 weeks thereafter until suspected radiographic progression. An early follow up clinical standard of care MRI will be performed 6 weeks (\pm 15 days) from the date of MRI showing suspected radiographic progression to confirm persistent radiographic progression. Clinical scans may be done more frequently, based on physician's discretion. Each MRI scan will be evaluated for progression.

Additional ferumoxytol steady state MRIs will be done at baseline, 12 weeks after radiation, at suspected radiographic progression and within 6 weeks (\pm 15 days) from suspected radiographic progression to confirm persistent radiographic progression.

When persistent radiographic progression is confirmed, subjects will be evaluated for a craniotomy with intent to complete resection and /or biopsy of the enhancing lesion, if this is thought to be the clinical standard of care.

Biopsy tissue obtained from surgery at persistent radiographic progression will be evaluated by the pathologists at OHSU. The pathologist will determine if the tissue is consistent with progression or pseudoprogression, where progression is defined as presence of viable metastatic carcinoma in the biopsy tissue and absence of tumor cell is assumed to reflect pseudoprogression. If histopathology confirms pseudoprogression the subject will continue on pembrolizumab every 3 weeks until further radiographic progression is suspected. If histopathology confirms progression, the subject will be removed from the study, followed clinically with serial clinical stand of care MRIs every 3 months for up to a year and then every 6 months until death or lost to follow-up.

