7.4 Trial Procedures

See the Schedule of Events for when tests should be completed.

7.4.1 Clinical procedures:

- Demographics
- Medical history
- Prior medication review
 - The investigator or qualified designee will review prior medication and herbal and dietary supplement use, including any protocol-specified washout requirement, and record prior medication taken by the subject within 28 days before starting the trial. Treatment for the disease for which the subject has enrolled in this study will be recorded separately and not listed as a prior medication.
 - The investigator or qualified designee will record medication, if any, taken by the subject during the trial. All medications related to reportable SAEs and ECIs should be recorded as defined in Section 7.2.
 - Subjects will be asked to stop all nonprescription herbal supplements and over the counter medication.
- Full physical examination
- Vital signs
 - temperature, pulse, respiratory rate, height, weight and blood pressure. Height will be measured at screening only.
- ECOG performance status (Appendix)
- Archival tissue collection:
 - If available, any tumor biopsy tissue (lung, mediastinal, or brain) that was obtained prior to screening for the study will be requested and sent to the Merck-designated Contract Research Organization (CRO) QualTek Molecular Laboratories for PD-1 biomarker assay.
- Biopsy or resection of metastatic brain lesion
 - When clinically indicated, a biopsy or resection will be done of the brain lesion(s) 1) prior to enrollment and SRS, and 2) at the time of persistent radiographic progression. Any tumor biopsy tissue will be sent to the Merck-designated Contract Research Organization (CRO) QualTek Molecular Laboratories for PD-1 biomarker assay.
- Radiation therapy:
 - All patients will receive standard of care stereotactic radiosurgery in 1-5 fractions, at the discretion of the treating radiation oncologist. If all lesions cannot be treated on the same day, all lesions MUST be treated ≤ 14 days of treatment of the first lesion. Gamma knife or X-rays with nominal energy of 4 megavoltage (MV) or greater for accelerator-based treatments, including

isocentric conical collimators, mini-multi-leaf (5 mm or less) technology or linear accelerators mounted on robotic arms will be used to deliver the target dose.

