8.5.2 Tissue Biomarkers

PD-L1 testing will be performed by the CRO QualTek Molecular Laboratories. Any archived tissue samples or tissue obtained from brain biopsy prior to enrollment (archival tissue) and those obtained at suspected radiographic progression will be sent to the CRO for PD-L1 expression assay. We will correlate outcomes and imaging findings with PD-L1 expression in archival systemic tumor tissue, brain biopsy prior to enrollment, and tissue obtained at persistent radiographic progression. Frozen tissue and fixed tissue blocks from initial lung biopsies will be used. In a subset frozen sections and fixed tissue blocks from subjects who undergo resection of brain metastases for clinical indications will also be utilized.

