Among the 20 subjects, 5 to 10 subjects are expected to have data on PD-1 receptor expression (Yes vs. No) and immune cells (T cells, CD4+, CD8+, macrophages, M1, M2 etc) before initiation of Pembrolizumab and at the time of progression. If data allow, we will compare the PD-1 receptor expression and immune cells data before initiation of pembrolizumab and at the time of progression using exact McNemar's test or Wilcoxon signed test to accommodate the paired nature of the data.

Lastly, in subjects with measurable systemic lesions, vascular volume fraction (VVF), vessel size index (VSI) and vessel density index (VDI) will be measured and compared between subjects with true vs. pseudoprogression, if data allow.

In summary, all these proposed analyses will be conducted on an exploratory basis. A two-sample t-test may be used if the data show adequate normality. We will only provide descriptive statistics if the comparison mentioned above will not yield clinical meaningful

results. The purpose of these exploratory analyses is to see whether some preliminary signals in the data could be detected.

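### The before/after tissue comparison does not separate same-site from cross-site pairs, so a difference between lung or mediastinal tissue and brain could be read as a change after therapy

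*Combined protocol and SAP*

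**What the plan says.** **Objective.** Exploratory objective 3 in Section 3.0 reads: "Compare the changes percentage expression in PDL-1 in the biopsy tissue before and after therapy at the time of progression". It names no site. The rationale adds that PD-L1 expression and immune cell types "will be compared between archival biopsy tissue and brain tumor tissue obtained before initiation of pembrolizumab and at the time of progression".

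**Tissue before therapy.** Section 7.4.1 requests, where available, "any tumor biopsy tissue (lung, mediastinal, or brain) that was obtained prior to screening". Section 8.5.2 states: "Frozen tissue and fixed tissue blocks from initial lung biopsies will be used". It then adds: "In a subset frozen sections and fixed tissue blocks from subjects who undergo resection of brain metastases for clinical indications will also be utilized". Footnote 1 to the Schedule of Events makes brain surgery before enrolment optional.

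**Tissue at progression.** Section 7.2 describes evaluation for a "craniotomy with intent to complete resection and /or biopsy of the enhancing lesion" once persistent radiographic progression is confirmed. This sample is therefore brain.

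**Analysis.** In Section 10.2, "5 to 10 subjects are expected to have data on PD-1 receptor expression" and immune cells at both time points. If data allow, the plan will "compare the PD-1 receptor expression and immune cells data before initiation of pembrolizumab and at the time of progression" using exact McNemar's or a Wilcoxon signed test. No section requires the two samples of a pair to share a site or lesion, and none separates pairs by site.

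**The concern.** A paired test removes differences between subjects. It does not remove a difference between the two samples that has nothing to do with time. If the earlier sample is a lung biopsy and the later one a brain metastasis, the within-subject difference contains both the change over time and the difference between organs. This holds for any marker and for either test.

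Objective 3 is about change before and after therapy, and Section 10.2 says these analyses are there to look for preliminary signals. A systematic difference between primary and metastatic tissue, in the marker or in infiltrating immune cells, could supply such a signal without any change on therapy. It could also hide a real one. The primary sensitivity and specificity analysis and the secondary endpoints do not use this comparison.

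**Working it through.** **1. Which pairs are possible.** Before: lung, mediastinal or brain (Sections 7.4.1 and 8.5.2). At progression: brain (Section 7.2). Three combinations are allowed, and two of them cross sites.

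**2. What a pair measures.** For a subject whose earlier sample comes from site s:

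after(brain) − before(s) = [after(brain) − before(brain)] + [before(brain) − before(s)]

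The first bracket is change over time in brain. The second is the site difference, and at the organ level it is zero only when s is brain. If a fraction f of pairs is cross-site and the change over time is the same in all pairs, the expected difference is (change over time) + f × (site difference). McNemar's and the Wilcoxon signed test see only the total. With f = 1 the two parts cannot be separated at all. With f between 0 and 1 they can be separated only by splitting the pairs by site.

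**3. The plan's own figure.** The 5 to 10 subjects in Section 10.2 come without a formula or inputs, so the figure cannot be reproduced. The documents give neither the number with brain tissue at both times nor a lung-brain discordance rate.

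**4. Illustration under assumed rates.** None of the following rates is in the documents. Assume a yes/no marker and no change over time. Cross-site pairs go from positive to negative with probability a = 20%, 40% or 60%, and from negative to positive with probability 5%. Brain-brain pairs change 5% each way. Then

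- P(+ to −) = f·a + (1 − f)·0.05, and P(− to +) = 0.05
- apparent net loss = f·(a − 0.05)

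| f | a | Apparent net loss | Pairs out of 10 | Chance of exact McNemar p ≤ 0.05, n = 10 |
|---|---|---|---|---|
| 1 | 20% | 15 points | 1.5 | 0.5% |
| 1 | 40% | 35 points | 3.5 | 12.4% |
| 1 | 60% | 55 points | 5.5 | about 46% |
| 0.5 | 20% | 7.5 points | 0.75 | 0.04% |
| 0.5 | 40% | 17.5 points | 1.75 | 0.9% |
| 0.5 | 60% | 27.5 points | 2.75 | 5.2% |
| 0 | any | 0 | 0 | under 0.01% |

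The chances come from full enumeration of the discordant pairs. Reversing the assumed direction turns the loss into a gain of the same size.

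**5. The lower end of the range.** With d discordant pairs all in one direction, the exact two-sided McNemar p is 2 × 0.5^d. This gives 0.0625 for d = 5 and 0.031 for d = 6. With five pairs the test cannot reach 0.05, so any distortion there lies in the reported change and not in the p-value.

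**The case against.** **Section 10.2 does not say that sites are pooled.** A reader might infer that every pair, whatever its site, goes into one test. The text does not say so. It is silent on which tissue forms the earlier sample, and Section 7.4.1 is a collection rule with no pairing rule. Section 8.5.2 names archival systemic tissue, brain biopsy before enrolment and tissue at progression as three sources, and the rationale in Section 3.0 can be read as keeping archival and brain tissue apart. This part of the objection stands. But Section 8.5.2 makes the distinction only for correlation with outcomes and imaging, and it is not carried into Section 10.2. Following the plan as written can still produce cross-site pairs.

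**Most pairs may be brain-brain.** Section 10.1 assumes 15 subjects have surgery, and Section 5.1 requires histological confirmation and a PD-L1 result. If any lung block counted, more than 5 to 10 pairs might be expected, so the lower figure could mean a narrower set. It could equally reflect limited tissue availability. The documents do not settle this, so they do not support saying that most pairs will be lung-brain, nor the opposite.

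**Same-site pairs do not isolate pembrolizumab.** This is correct. There is no control group. All subjects receive radiosurgery, and chemotherapy, bevacizumab or steroids may be given. Prior PD-(L)1 inhibitors are allowed. The second sample exists only in those who progress and may come from a different lesion. Restricting to brain-brain pairs removes one avoidable influence and leaves these.

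**The analysis is exploratory.** It is, and this limits the weight of the point. The fallback to descriptive statistics does not resolve it, because a descriptive before/after change across sites mixes organ and time in the same way.

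**Conclusion.** The point holds as a gap in the analysis rule. The plan permits cross-site pairs and gives no instruction to separate them, so a site difference could be reported as change after therapy. Nothing in the documents supports a stated size, direction or frequency, and the table above shows only what assumed rates would imply. Full confounding would arise only if all pairs were cross-site, which the documents neither state nor exclude. The consequence is confined to exploratory objective 3. This is a worthwhile low-cost improvement and not a threat to the trial's main results.

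**What to change.** In Section 10.2, before the tissue data are analysed:

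- Record the site, lesion and date of each sample. Section 7.4.1 sets no age limit on archival tissue, so an old block may also predate earlier systemic therapy.
- Base the before/after paired comparison on brain-brain pairs, and note whether both samples come from the same lesion.
- List lung-brain and mediastinal-brain pairs separately and descriptively, and do not call them change on therapy.
- Restate the expected number of pairs, now 5 to 10, for brain-brain pairs.
- Describe even the brain-brain result as change between baseline and progression after radiosurgery plus pembrolizumab and any concomitant therapy.

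This takes a few sentences. Site and date should already be on the pathology report, and no new procedure is needed. The cost is fewer pairs, possibly so few that only a listing remains. Making the change before results are seen avoids choosing pairs by their outcome.

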7.4.3 Imaging

Standard of care clinical brain MRI: Clinical MRIs are done at baseline, 12 weeks post radiation and then every 9 weeks (see special instructions below for evaluating persistent radiographic progression). Gadolinium is the preferred contrast agent, when subject qualifies (per institutional policy) for gadolinium infusion, but it is not required. Clinical scans may be done more frequently, at physician's discretion. Each MRI scan will be evaluated for progression.

Ferumoxytol MR: ferumoxytol steady state MRIs of the brain are done baseline, 12 weeks post radiation, anytime there is suspected radiographic progression and 6 weeks after suspected radiographic progression. Additional MR imaging of systemic lesions may be performed in the same setting and time points as the brain imaging. Details are explained in section 8.4.2. Blood pressure and pulse will be taken at the start of MRI (\pm 5 minutes), after each ferumoxytol injection (\pm 5 minutes), and again 30 minutes (\pm 5 minutes) after the first injection of ferumoxytol.

Evaluation of systemic disease burden: A standard of care PET/CT or CT abdomen, chest and pelvis with contrast will be obtained within 3 months of enrollment and at least every 6 months thereafter. This is considered standard of care for patients with NSCLC. Stable systemic disease burden should be demonstrated at enrollment and for continuation of study drug.

7.4.3.1 Imaging instructions for evaluating persistent radiographic progression:

If there is suspected progression, subjects undergo a ferumoxytol steady state MRI and continue on pembrolizumab for two more cycles (total of 6 weeks). At the 6 week point, clinical standard of care and ferumoxytol MRIs will be repeated to confirm persistent radiographic progression. If the 6 week scan confirms progression, then pembrolizumab is discontinued and subject is evaluated for surgery. If histopathology confirms pseudoprogression, the subject will continue on pembrolizumab every 3 weeks until further radiographic progression is suspected. If histopathology confirms progression, the subject will be removed from the study.

7.4.4 Adverse Event Monitoring

The investigator or qualified designee will assess each subject to evaluate for potential new or worsening AEs as specified in the Schedule of Events and more frequently if clinically indicated. Adverse experiences will be graded and recorded throughout the study and during the follow-up period according to NCI CTCAE Version 4.0. Toxicities will be characterized in terms regarding seriousness, causality, toxicity grading, and action taken with regard to trial treatment. All AEs will be attributed to pembrolizumab or ferumoxytol separately.

For subjects receiving treatment with pembrolizumab all AEs of unknown etiology associated with pembrolizumab exposure should be evaluated to determine if it is possibly an event of clinical interest (ECI) of a potentially immunologic etiology (termed immune-related adverse events, or irAEs)

Please refer to Section 9 for detailed information regarding the assessment and recording of AEs.

7.4.5 Post-study anticancer therapy status

The investigator or qualified designee will review all new anti-neoplastic therapy initiated after the last dose of trial treatment. If a subject initiates a new anti-cancer therapy within 30 days after the last dose of trial treatment, the 30 day Safety Follow-up visit must occur before the first dose of the new therapy. Once new anti-cancer therapy has been initiated the subject will move into survival follow-up.

7.4.6 Safety Follow-Up Visit: 30 days post discontinuation

The mandatory Safety Follow-Up Visit should be conducted approximately 30 days after the last dose of trial treatment or before the initiation of a new anti-cancer treatment, whichever comes first. All AEs that occur prior to the Safety Follow-Up Visit should be recorded. Subjects with an AE of Grade > 1 will be followed until the resolution of the AE to Grade 0-1 or until the beginning of a new anti-neoplastic therapy, whichever occurs first. SAEs that occur within 90 days of the end of treatment or before initiation of a new anti-cancer treatment should also be followed and recorded. Subjects who are eligible for retreatment with pembrolizumab (as described in Section 7.4.9) may have up to two safety follow-up visits, one after the Treatment Period and one after the Second Course Phase.

